The objectives of this study are to clarify: what are the most salient social-ecological risk and resilience factors that should serve as targets for interventions and who are the survivors most at risk to be recruited for future interventions, how survivors want to receive educational interventions, and which educational interventions are most effective. Using a cross-sectional cohort study of 18-25 year old childhood cancer survivors and/or their parents, this study will determine predictors of transition readiness (Aim 1) and predictors of adherence to adult survivor-focused healthcare (Aim 2), as well as evaluate the quality (Aim 3) and efficacy (Aim 4) of electronic educational interventions for AYA survivors. The specific aims are to:

Aim 1: Evaluate social-ecological factors among AYA childhood cancer survivors participating in pediatric survivor care to determine factors associated with decreased transition readiness (i.e., risk factors) and increased transition readiness (i.e., resilience factors), as well as characterize patterns of co-occurring risk factors associated with transition readiness.

Aim 2: Evaluate social-ecological factors among AYA childhood cancer survivors following transfer to identify factors associated non-adherence (i.e., risk factors) and adherence (i.e., resilience factors) to adult survivor care, as well as characterize patterns of co-occurring risk factors associated with non-adherence to adult survivor care.

Aim 3: Develop and assess quality of electronic multimedia materials to educate AYA survivors about lifelong survivor care through qualitative interviews with AYAs.

Aim 4: Evaluate the impact of electronic educational materials on AYA survivors' knowledge about late effects, perceived benefits, self-efficacy, and intentions to engage in lifelong survivor care.

III. Study Design

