- *A2 Hypothesis 4:* When individual risk factors for non-adherence are included in principal component analyses (PCA), 2 or more components will emerge indicating subgroups at risk for poor transition outcomes.

Aim 3 Hypothesis:

- *A3 Hypothesis:* Stakeholder input and review of electronic media developed in this study using qualitative methods will increase acceptability and value to AYA survivors of childhood cancer

Aim 4 Hypotheses:

- *A4 Hypothesis 1:* Exposure to multimedia educational materials will significantly increase AYA survivors' knowledge about late effects and surveillance.
- *A4 Hypothesis 2:* Exposure to multimedia educational materials will significantly increase AYA survivors' perceived benefits of, self-efficacy to, and intentions to engage in survivor care across the lifespan.

A. Outcomes

For Aim 1, our metrics of “transition readiness” will be determined by patient- and parent-reported scores from the Readiness for Transition Questionnaire (RTQ-Overall). The RTQ-Overall assesses perceived preparedness to transfer both healthcare responsibility (from parent to teen) and services (from pediatric to adult care), with higher scores indicating increased transition readiness. For Aim 2, we will operationalize “adherence to adult survivor-focused healthcare” as the attendance of at least one healthcare visit with an adult provider focused on survivorship within 18 months following transfer from pediatric care. This operationalization of adherence was chosen based on recommendation by COG that survivors of childhood cancer should be evaluated annually and has been previously utilized to classify survivor clinic attendance. For participants who report attending an adult survivor care appointment, we will obtain a medical record release to verify date and attendance at an appointment with the adult survivor care provider. For Aim 3, we will elicit stakeholder feedback on the content, clarity, style, and interest-level of the electronic educational materials. For Aim 4, AYA health beliefs, knowledge

about survivor care and late-effects, patient activation, and self-efficacy and intentions to engage in lifelong survivor care will be evaluated using patient reported outcome (PRO) measures. In addition, a 15-item multiple choice quiz will be utilized to assess participants' knowledge of the content covered in the electronic educational materials.

B. Setting & Participants

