DISSEMINATION: Share AYA educational material via implementation toolkits (R01 CA218389-01) & Post material on www.cancersurvivorlink.org educational platform & share with registrants via email

For Aim 3, eligible stakeholders will be recruited (N=20 AYA survivors) via phone or in clinic by a member of the Aflac Cancer Survivor Research team, and survivors interested in participating will be verbally consented via WebEx. Example questions are outlined in Table 3. These stakeholder reviews will be used to inform revisions to the infographics and videos, which will be made prior to engaging in Aim 4.

For Aim 3 and 4, all interviews will be recorded for transcription/qualitative data analysis.

The consent and interview processes in Aim 3 will be completed sequentially during the subject's webex interview; therefore, this consent discussion will be recorded. All Aim 3 subjects must verbally consent to this recording prior to the recorded consent process. Once the subject has consented to recording, the recording will begin. The study staff will follow Aim 3 telephone scripts for the entire consenting process. Telephone scripts for Aim 3 are included in this protocol.

Once the interview recording begins, study staff will ask if the subject has provided recording consent (for documentation purposes). Next, all subjects will have to confirm their identity (for security and data validity purposes) by providing their name and date of birth. The information provided by the subject must match the information gathered in Epic for the main study consenting to begin. Subjects will then go over the main study and verbally consent for their participation in it.

For Aim 4, we will recruit a total of N=58 AYA survivors to evaluate our revised electronic educational materials (eligibility requirements described above). Recruitment procedures will be the same as in Aim 3 except that in Aim 4, subjects will review and complete consent online as in Aims 1 & 2. The initial page of the REDCap survey will contain a brief online consent outlining the purpose of the study, its voluntary nature, time commitment,

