incentive information, release of PHI, and contact information of PI and Emory IRB should a participant have questions. To record participants' consent to participate, we will have them click a radio button labeled "Yes, I agree to take part" or "No, I do not want to take part". We will also have participants insert the current date. Participants who select "Yes, I agree to take part" will be routed to the study survey battery following their typed signature. Participants who select "No, I do not want to take part" will exit the REDCap system and route to a screen that thanks them for their consideration. Copies of the online consent from REDCap are attached with this protocol.

After consenting to Aim 4, participants will be asked to complete an online pre-test survey via REDCap. The pre-test will be the first step in a survey queue from REDCap. After subjects complete the pretest, the queue will allow them to review the materials that were created for Aim 4 within the REDCap platform. If the survey queue is started but not finished, study staff may contact the consented subjects via phone call, text or email in order to remind them to finish. Study staff will confirm receipt and review of material and schedule a post-test survey to be completed in REDCap two weeks after material is reviewed (the date when initial survey queue is completed).

These pre- and post-tests will be designed to assess AYA health beliefs, knowledge about survivor care and lateeffects, and self-efficacy and intentions to engage in lifelong survivor care. We have selected scales to assess participants' health beliefs and intentions (Table 3, and will generate a 15-item multiple-choice quiz to assess participants' knowledge of the content covered in the electronic educational materials). The pre- and post-test should take approximately 20-25 minutes each to complete. Up to five reminders will be sent to ensure survey completion.

At the time of initial consent for Aim 4, subjects will have the option to participate in telephone exit interviews via Zoom (N=25), lasting 30 minutes. All Aim 4 exit interviews will be recorded for transcription purposes and conducted 2-3 weeks following completion of the post-test. Example questions are outlined in Table 3.

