AYA Healthcare Responsibility	Readiness for Transition Questionnaire (RTQ)- Adolescent Responsibility
Parent & Family Factors	
Parent Psychosocial functioning: Anxiety, Depression, Post-Traumatic Stress Symptoms, Self-Esteem, Social functioning	PROMIS Anxiety/Depression Impact of Events Scale-Revised (IES-R) Posttraumatic Growth Inventory (PTGI) Rosenberg Self-Esteem Scale NIH Friendship - Fixed Form
Parent Health Beliefs: Perceived Benefit of Survivor care; Perceived Vulnerability to Late-effects	Benefits Scale for Survivor Screening Absolute Perceived Vulnerability
Family Functioning: Parental Involvement in Healthcare; General family functioning	RTQ-Parent Involvement Family Assessment Device (FAD)
Family SES: Income; AYA Financial Support Parent education	Demographics Questionnaire
Provider & System Factors	
Patient Satisfaction: Accessibility & Convenience; Communication; Autonomy Support	Patient Satisfaction Questionnaire (PSQ) Health Care Climate Questionnaire (HCCQ)
Access to care issues: Insurance status; Geographic distance, neighborhood-level social determinants	Demographics Questionnaire

Aims 3 & 4: We will accomplish aims 3 and 4 by conducting a comprehensive formative evaluation of interactive infographics and videos designed to educate young adult survivors about the impact of childhood cancer

treatment on future health and subsequent need for survivor care across the lifespan. As part of our formative evaluation process, we will seek feedback and revisions from stakeholders (Aim 3), test the effectiveness of these materials with regard to improving knowledge, perceived benefits, self-efficacy, and intentions with AYA survivors through a pretest posttest design (Aim 4), and solicit AYA feedback for additional improvements through exit interviews (Aim 4).

Table 3 outlines the modifiable variables we will measure along with the methods and instruments we will use to measure these variables. After patients have consented and before they review the learning materials, they will complete a pre-test online. Later, after viewing the materials, they will take a post-test online. The questionnaires will be administered electronically using the REDCap platform. The surveys will take about 20-35 minutes to complete. Copies of the pre and post-test surveys from REDCap for Aims 3 & 4 are attached with this protocol.

Table 3. Methods and Measures (Aims 3 & 4)

Quantitative Measures		

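### Aim 4's efficacy and most-effective wording goes beyond a single-group pre-post design, which can neither rank materials nor separate their effect from retest or outside learning

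*Combined protocol and SAP*

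**What the plan says.** **Claims.** Section II (Goals/Aims Overview) includes among the study objectives to clarify "how survivors want to receive educational interventions, and which educational interventions are most effective". It then says the study will "evaluate the quality (Aim 3) and efficacy (Aim 4) of electronic educational interventions for AYA survivors". In Section III, Aim 4 Hypothesis 1 is causal: "Exposure to multimedia educational materials will significantly increase AYA survivors' knowledge about late effects and surveillance". Hypothesis 2 says the same of perceived benefits, self-efficacy and intentions. Section III.D (Aims 3 & 4) says the effectiveness of the materials will be tested "through a pretest posttest design (Aim 4").

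**Design.** Section III.C states that "we will recruit a total of N=58 AYA survivors to evaluate our revised electronic educational materials". Each participant takes a pre-test, reviews the materials, and takes a post-test two weeks after review. No control, delayed-access group, randomisation or second version of the materials is described.

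**Instrument.** For knowledge, the team "will generate a 15-item multiple-choice quiz to assess" the content covered. Table 3 has one 15-item knowledge entry, listed for both pre-test and post-test.

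**Analysis.** Section VI (Aims 3 & 4) compares before with after by paired t-tests or Wilcoxon signed-rank tests. The ANOVAs and independent t-tests in that section compare participant subgroups, not materials.

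**The concern.** The stated conclusions are of two kinds that the design cannot deliver.

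1. *Ranking.* Finding the most effective intervention requires at least two interventions to be compared. Aim 4 is the only aim that measures effect, and everyone in it receives the same package.
2. *Attribution.* Efficacy and the causal hypotheses require the change to be due to the materials. In one uncontrolled group, the paired difference also contains whatever comes from having seen the questions, from looking things up afterwards, and from other learning between the tests. Nowhere does the plan name this as a limitation or restrict the conclusion to within-group change.

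What is at stake is the reported conclusion: a significant paired test would be read as efficacy when ordinary retest gain can produce it.

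**Working it through.** **Inputs from Section VI (Aims 3 & 4):** n = 58; SD of the paired difference 4.0 points; significance level 0.05; target gain 1.5 points, also given as an effect size of 0.40; stated power above 80%. The section does not say whether the Aim 4 test is one- or two-sided; two-sided is assumed.

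**Step 1. Reproduce the plan's power.** For a paired t-test, power = P(T > t_crit), where T is noncentral t with df = n − 1 and noncentrality (gain/SD) × √n.
- df = 57, t_crit = 2.002.
- gain/SD = 1.5/4.0 = 0.375, which the plan appears to round to 0.40.
- noncentrality = 0.375 × √58 = 0.375 × 7.616 = 2.856.
- Power = 80.2%. At an effect size of 0.40 it is 85.0%.

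The stated figure holds. The issue is what the test can support.

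**Step 2. Same test, no effect of the materials.** Replace the 1.5-point effect by a gain g that comes only from retesting or outside learning. The documents give no value for g, so a range is assumed. The probability of a significant result *favouring the materials* is P(T > 2.002) with noncentrality (g/4.0) × 7.616.

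| Assumed g (points of 15) | g/SD | Noncentrality | P(significant in favour) |
|---|---|---|---|
| 0 | 0 | 0 | 2.5% |
| 0.25 | 0.0625 | 0.476 | 6.8% |
| 0.5 | 0.125 | 0.952 | 15% |
| 0.75 | 0.1875 | 1.428 | 29% |
| 1.0 | 0.25 | 1.904 | 46% |
| 1.5 | 0.375 | 2.856 | 80% |

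The right comparator is 2.5%, not 5%, because the error of interest lies in one direction. A 1.5-point retest gain cannot be told apart from the planned effect.

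**Step 3. Ranking.** Here no arithmetic applies. With one package and no comparison between packages, no contrast in Section VI corresponds to the ranking objective in Section II.

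**Step 4. What design remedies would take.**
- *Concurrent 1:1 control*, same 1.5-point difference in change, SD 4.0, two-sided 0.05, 80% power: n per arm = 2 × (1.960 + 0.842)² × 4.0² / 1.5² ≈ 112, so 224 in total. Splitting the planned 58 into 29 per arm gives about 29–30% power.
- *Five extra items that the materials do not cover*, used as a within-person contrast. The SD of the covered gain is 4.0/15 = 26.7 percentage points. For five items at 50% correct with binomial noise only, the SD of the uncovered gain is 100 × √(2 × 0.25/5) = 31.6 points; 40 is taken as a less favourable value. The target is 1.5/15 = 10 points. The SD of the contrast is √(26.7² + s² − 2r × 26.7 × s), where s is the uncovered SD and r the correlation between the two gains. With n = 58, s = 31.6 gives 44%, 58% or 72% power at r = 0, 0.3 or 0.5; s = 40 with r = 0 gives 34%. All values of s and r are assumed.

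**The case against.** The best defence is that this is formative work. Section III.D calls it a formative evaluation, Aim 4's own wording in Section II speaks of impact, and the ranking phrase is a study-level objective rather than part of Aim 4. A single-group pre-post design is common at this stage, and the exit interviews ask what participants learned from the materials. This stands as a defence of the *design*. It does not remove the efficacy label, the ranking objective or the causal hypotheses, and interviews do not replace a comparison.

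A reader might infer more than the documents support:

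- *That the identical quiz is certainly given twice.* This is a reasonable inference from one 15-item entry and no alternate form, but the items are nowhere said to be identical, and the attached surveys are not in the text available here.
- *That a false positive would trigger dissemination.* Table 1 and Section III.C have the materials revised from both quantitative and qualitative data and then disseminated. Neither makes this depend on significance.
- *That the quiz is unwritten, so control items cost almost nothing.* Section III.C says the quiz will be generated, but Section III.D says the pre- and post-test surveys are attached. If the items exist, the instrument would have to be changed.
- *That a control arm or control items are required.* A control arm would need about four times the sample. The uncovered-item contrast has low power, assumes equal retest gain on both item sets, and leaves beliefs, self-efficacy and intentions untouched. Reasonable statisticians would disagree about it.

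**Conclusion.** The mismatch between claims and design is real and should be corrected. That Aim 4 cannot rank interventions, or isolate the effect of the materials, follows from the described design without any assumption. The size of the second problem does rest on assumptions: with no true effect, retest gains of 0.5 to 1.0 points would give a favourable significant result in about 15% to 46% of studies rather than 2.5%, using the plan's n = 58 and SD 4.0, a two-sided test, and gains that the documents do not provide. The power statement is sound for within-group change, and the design is acceptable for that purpose. This is a fault in the stated conclusions, not a reason to redesign the study.

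**What to change.** 1. Section II: delete "which educational interventions are most effective" from the objectives. Replace the efficacy label for Aim 4 with *pre-to-post change after review of the materials*.
2. Section III, Aim 4 Hypotheses 1 and 2: restate as expected within-group change from pre-test to post-test.
3. Section III.D: bring the effectiveness wording for Aim 4 into line with this.
4. Section VI: add a sentence that, without a comparison group, retest and outside learning cannot be excluded as explanations for change in the knowledge and belief outcomes.

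The cost is a more modest stated conclusion; sample size, schedule and analysis do not change. Items not covered by the materials could be added as an exploratory contrast reported beside the raw gain, but this is an optional, low-power design choice and not a required correction.

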No biological specimens will be collected as part of this research. Participants' electronic medical records will be reviewed to abstract treatment data. Confidentiality within this study will be rigidly maintained. Computer files will use study identification numbers only and are password protected. Only necessary personnel will have access to any of these files. Based on existing best practices for security and privacy in health information technology, we will identify the technologies and features to be employed to ensure privacy and security of personal information. This will address identity and access management, secure storage, secure messaging, encryption, and other security technologies and approaches.

VI. Statistical Analysis Plan

Aims 1 & 2: In 2015, the Aflac Cancer Survivor Program (Aflac CSP) saw over 200 AYA survivors aged 18-22 years (Aim 1). Additionally, the Aflac CSP has transitioned approximately N=165 survivor patients since 2013 (Aim 2). Based on our previous research with survivor patients > 18 years of age, we estimate that less than 2% of AYAs will be non-English speakers. During the year-long study period, we anticipate that there will be at least N=200 AYA patients who are eligible for participation in Aim 1 and at least N=160 AYA patients who are eligible for participation in Aim 2. Previous studies with our AYA population have yielded initial recruitment rates and retention rates above 80%. Of the eligible AYA patients, we estimate that 75% [Aim 1: N=220 patient-parent dyads (440 participants), Aim 2: N=120 patient-parent dyads (240 participants), Aim 3: N= 20 patients, Aim 4: N=58] will participate in each aim of the study. In our univariate analysis, these sample sizes provide us with at least 80% or greater power to detect correlations of magnitude ≥ 0.25 and odds ratios of at least 2.5, depending on the prevalence of the risk factor, assuming that approximately 20-30% of patients meet our definition of successful transition. Power analyses were conducted using PASS v. 11 (Kaysville, UT) using a two-sided test for a single correlation and a two sample Z-test for proportions. Given these anticipated numbers, we can assess at most 15 possible predictors for aim 1 and 12 predictors for aim 2 to ensure that we have at least 10 observations per predictor in our principal component analysis.

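### The Aim 1 sample of 220 dyads is presented as 75% of eligible patients, but 75% of the stated 200 is 150, and the 15-predictor limit also corresponds to 150

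*Combined protocol and SAP*

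**What the plan says.** All the figures are in one paragraph of Section VI (Statistical Analysis Plan), under Aims 1 & 2.

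- **Source population, Aim 1.** In 2015 the clinic "saw over 200 AYA survivors aged 18-22 years (Aim 1".
- **Eligible pool.** The expectation for Aim 1 is worded as a minimum: "we anticipate that there will be at least N=200 AYA patients who are eligible for participation in Aim 1". For Aim 2 the corresponding minimum is 160.
- **Participation rate and resulting samples.** The plan puts both in one sentence: "we estimate that 75% [Aim 1: N=220 patient-parent dyads (440 participants), Aim 2: N=120 patient-parent dyads (240 participants". The same bracket goes on to list 20 patients for Aim 3 and 58 for Aim 4.
- **Predictor limit.** From these numbers, "we can assess at most 15 possible predictors for aim 1 and 12 predictors for aim 2", so that the principal component analysis has no fewer than 10 observations per predictor.
- **Power.** One statement covers both aims: 80% or more for correlations of 0.25 and above, from a two-sided test of a single correlation.

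**The concern.** The paragraph is a short chain: pool times rate gives the sample, and the sample divided by 10 gives the predictor limit. Aim 2 runs through the chain without a break. Aim 1 does not. Its stated sample exceeds the only pool figure given, and its predictor limit corresponds to a different, smaller sample.

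Two things depend on which number is meant. The first is the recruitment target, 440 participants or 300, and whether the clinic can supply it. The second is how many variables may enter the principal component analysis. Table 2 in Section III.D names 18 patient scales (counting the PROMIS anxiety and depression forms separately), before demographics and the parent, family and system factors. A limit of 15 or of 22 could therefore decide what is kept after the screen at the 0.1 level.

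**Working it through.** **Inputs, all from Section VI, Aims 1 & 2:** eligible pool 200 (Aim 1) and 160 (Aim 2), both given as minimums; participation 75%; stated samples 220 and 120 dyads; stated predictor limits 15 and 12; at least 10 observations per predictor; target correlation 0.25, two-sided test. Alpha is not stated for Aims 1 and 2, so 0.05 is assumed.

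**Step 1. Sample = pool × rate.**
- Aim 2: 160 × 0.75 = 120. This reproduces the plan.
- Aim 1: 200 × 0.75 = 150. The plan says 220, and 220 / 200 = 110%.

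**Step 2. Can another rate give 220 from 200?** Rates of 80%, 85%, 90% and 100% give 160, 170, 180 and 200. Removing the 2% upper estimate for non-English speakers gives 200 × 0.98 × 0.75 = 147. None reaches 220.

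**Step 3. Pool needed for 220.** At 75%: 220 / 0.75 = 293.3, so 294 patients. At 80%, the level the plan says its earlier recruitment exceeded: 220 / 0.80 = 275.

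**Step 4. Predictor limit = sample / 10.**
- Aim 2: 120 / 10 = 12. This reproduces the plan.
- Aim 1 at 150: 150 / 10 = 15. This reproduces the plan.
- Aim 1 at 220: 220 / 10 = 22. This does not.

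Two separate routes (200 × 0.75, and 15 × 10) arrive at 150. The documents never print 150; it is inferred from the arithmetic.

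**Step 5. Size of the gap.** 220 − 150 = 70 dyads, or 140 participants; 70 / 220 = 32%.

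**Step 6. Effect on power.** By Fisher's z, power ≈ Φ(atanh(r) × √(n − 3) − 1.96), with atanh(0.25) = 0.2554. The smallest correlation with 80% power is tanh((1.96 + 0.842) / √(n − 3)).

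| Dyads | Power at r = 0.25 | Smallest r with 80% power | Predictors at 10 each |
|---|---|---|---|
| 150 | Φ(0.2554 × √147 − 1.96) = 0.872 | 0.227 | 15 |
| 220 | Φ(0.2554 × √217 − 1.96) = 0.964 | 0.188 | 22 |

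The Aim 1 power claim holds at both sizes.

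**The case against.** The strongest reply is that 200 is a minimum. The supporting count covers one year (2015) and ages 18 to 22, whereas Section III.B admits patients aged 18 to 25 seen at least once in the past two years, so the true pool could be larger. That stands as far as it goes: 220 is not impossible. It is unsupported, because 220 at 75% needs about 294 eligible patients and the documents give no such count. Transition out of the clinic before age 22 also limits what the wider age range can add.

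Second, 15 predictors with 220 dyads gives 220 / 15 = 14.7 observations each, so the rule of at least 10 is met. This also stands: a limit of 15 would be cautious rather than a breach. But the plan presents 15 as the maximum its numbers allow, and at 220 that maximum is 22.

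Third, the Aim 3 and Aim 4 figures in the same bracket have no stated pool behind them, so the bracket may partly be a list of targets. Aim 2 nevertheless fits the 75% rule exactly, and a target of 220 would still need reconciling with the stated pool and limit.

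Fourth, the plan does not say which sample went into the power calculation, and the joint claim for a correlation of 0.25 is governed by the smaller Aim 2 sample. Agreed: the Aim 1 power claim is not overturned. Restating the detectable correlation is for consistency.

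**Conclusion.** The concern holds. The stated Aim 1 sample of 220 dyads (440 participants) does not follow from the plan's own pool and rate, which give 150 dyads (300 participants), and it does not match the 15-predictor limit. The same arithmetic reproduces both Aim 2 figures, which supports reading 150 as the basis of the Aim 1 limit.

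At the stated minimum pool and 75% participation, Aim 1 falls 70 dyads (32%) short of its stated size; a larger pool would narrow that gap. If 220 is the real target, the limit of 15 is not the maximum it allows. The documents do not show which figure is intended.

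The consequence is limited to the enrolment target, its feasibility and the predictor limit. The 80% power claim for a correlation of 0.25 in Aim 1 stands at either size, under the assumed two-sided alpha of 0.05. The plan should be corrected, but the Aim 1 hypotheses and analysis method are unaffected.

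**What to change.** Put the Aim 1 pool, participation rate, sample size and predictor limit on one basis in Section VI, and state the alpha used. There are two ways:

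- **Keep the stated pool and rate.** Restate Aim 1 as 150 dyads (300 participants), with at most 15 predictors and 80% power for a correlation of about 0.23. This follows from figures already in the plan and is a text correction to one paragraph.
- **Keep 220 dyads.** Restate the eligible pool as about 294 or more, supported by an actual clinic count, with a predictor limit of 22 and 80% power for a correlation of about 0.19. A limit of 15 could be kept by choice, but it should then be described as a choice and not as the maximum. This option needs the sponsor to obtain the count as well as edit the text.

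Neither option adds patients to what the plan already states.
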